5.4.7 Bone Mineral Density

Bone mineral density z-scores will be summarized and analyzed in a manner similar to the standard laboratory evaluations.

5.4.8 Tanner Staging

The number and percentage of safety population subjects at each Tanner stage will be summarized treatment period and by visit according to treatment received during the period. Summaries will be repeated to reflect the use of Baseline 1 and Baseline 2, as defined in [Section 5.4.2](#).

5.4.9 Sterility Testing of EDS-EP

The number and percentage of potentially contaminated infusions at any time and potentially contaminated infusions by visit will be summarized by treatment period and visit, according to treatment received during the period and in total.

5.4.10 Process Events/Interruptions

The number of subjects with infusions, the number and percentage of subjects with infusions who experienced at least 1 process event, the number of process events, and the number and percentage of process events by root cause will be summarized by treatment period and visit, according to the treatment received during the period.

5.5 PK/PD Analysis

PK/PD analysis is not part of this statistical analysis plan.

5.6 Analysis of Other Assessments

Not applicable.

5.7 Interim Analysis

No interim efficacy analysis will be conducted in this study. Interim review of safety data is described in [Section 5.9](#).

5.8 Primary Analysis

The primary analysis based on 6-month initial treatment period (Visit 1 to Visit 9) data from all subjects will determine the success or failure of the trial. However, as per the design, subjects will continue in the trial beyond the initial treatment period (approximately six months), until subjects have been followed through the extension treatment period (Visit 9 – Visit 15). This will provide efficacy data beyond the primary analysis and will be considered exploratory, due at least in part to the placebo switching that will limit the power. To clarify, Section 11.2 of the protocol describes procedures “if one of the doses has been eliminated following the Interim Analysis.” This description relates to interim safety analyses and DSMB actions, not actions taken based on review of an interim efficacy analysis.

The blind will be broken after all subjects have completed the double-blind, Initial Treatment Period, and the database for this period has been locked, so that the primary efficacy analysis can be performed. The biostatistics team will prepare and quality check a blinded version of the primary analysis output, and then a second biostatistics team, otherwise uninvolved in the study and who will remain uninvolved in the study until after final database lock and unblinding, will run the quality checked primary analysis under unblinded conditions and distribute the results as instructed; all unblinded outputs will be generated into a restricted network area. To further ensure that the blind is maintained for the extension period, the following restrictions on communications within the CRO, and between the CRO and the Sponsor, will be put in place:

- The second, unblinded biostatistics team conducting the primary efficacy analysis will have no direct communication with any blinded personnel within the CRO or at EryDel, other than for purposes of oversight (such as providing any programming issues back to the blinded biostatistics team to address).
- Any communications or documentation generated during the primary efficacy analysis will be filed outside the Trial Master File (TMF) and will be incorporated into the TMF after final database lock (of extension treatment period data) to meet requirements of GCP. The nature of this repository will be agreed with the Sponsor in advance of the primary efficacy analysis.
- The Unblinded Biostatistics team conducting the primary efficacy analysis can only discuss with and provide results to the Chief Medical Officer and Head of Regulatory Affairs from EryDel.

Conduct of the primary efficacy analysis by the team who is to be unblinded will be conducted according to the PPD standard operating processes for determination of analysis populations and release of randomization codes and interim analysis.

5.9 Data Monitoring

An independent Data Safety Monitoring Board (DSMB) was established by EryDel to review the safety of all subjects enrolled in this trial, on an ongoing basis. No EryDel employee or investigator involved in the EDS-EP clinical studies is a member of this board. The DSMB periodically reviews the safety data accrued.

The DSMB met regularly to assess the safety from the emerging data. The first DSMB meeting was conducted prior to the start of the trial, and the DSMB decided when the first data review safety DSMB meeting would occur. DSMB meetings were held when 9 patients completed 30 days of treatment. In January 2020, the DSMB agreed to quarterly meetings.

The DSMB will be regularly notified of the occurrence of any fatal or life-threatening events within 7 calendar days and any other serious adverse events within 15 calendar days. The DSMB will also receive updates on any adverse dropouts on a regular basis (once per month). The DSMB will have access to the blinded safety data including serious AEs and adverse dropouts, as well as clinically significant abnormal laboratory tests, vital signs, and ECGs at periodic intervals. The DSMB may request an unblinding of the treatment groups if there is a safety concern.

The DSMB will review all of the safety data on an ongoing basis, with special emphasis on the incidence and severity of steroid related events, new infections, and serious AEs and deaths, in addition to the standard safety parameters. The Board will make a recommendation to EryDel to (a) amend the ongoing study (e.g., increase safety monitoring), (b) terminate the EDS program (e.g., the EDS-EP safety profile is unacceptable), or (c) continue the clinical program as designed. The current study protocol will not be amended or changed (this includes the study design and entry criteria) unless mandated by the emerging (unblinded) safety profile of EDS-EP.

Details of the DSMB charter (separate document) will be submitted to regulatory authorities and will be available to Ethics Committees/IRBs upon request.

5.10 Changes to Methods Planned in the Protocol

Per protocol, sensitivity analyses are planned using three methods: LOCF, OC, and OC+RDO (observed cases plus retrieved dropouts). Each method handles missing values differently. LOCF imputes missing values by using last observation carried forward, while OC does not impute values but instead uses only observed cases. Per protocol, “Those patients who discontinue treatment prematurely but return for scheduled efficacy assessments at 6, 9 and 12 months are defined as RDOs.” According to this definition, none of these subjects would be excluded from any of the four analysis populations, and since all have efficacy assessments at three of the four ICARS time points (only missing Visit 6 [“Month 3”]), they would be included in the OC analysis (as well as all other analyses). Although RDO subjects with missing evaluations at the Visit 6 (“Month 3”) ICARS time point will not contribute a Visit 6 (“Month 3”) ICARS evaluation in the OC analysis, they will be included in the LOCF analysis. Hence, the use of the LOCF and OC methods will sufficiently incorporate the RDO subjects, and therefore the third sensitivity analysis (OC+RDO) will not be employed.

Due to deviations in the timing of the visits, the total months of treatment and assessments exceeded the 12 months as described in the protocol. The data as collected by the investigators will still be included and analyzed.

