5.1.3 Handling Missing Data

Baseline Values

If values are missing at the baseline visit (Day 0/1), and the data are also recorded at screening, then the screening value will be used in the summaries and calculations of change from baseline. Otherwise, the baseline value will be missing for safety and efficacy endpoints.

Missing Efficacy Assessments

The missing data methods are an integral part of the data analysis for efficacy and are described in full in [Section 5.3](#). For the primary analyses of mICARS, the use of a mixed-effect model repeated measure (MMRM) model allows for missing data and assumes the data are missing completely at random (MCAR), so no imputations will be performed.

For sensitivity analysis, several multiple imputation methods will be used:

1. Impute all missing data within the original treatment group.
2. Impute all data missing due to COVID-19 related restrictions to the original treatment group and impute from the control group (Jump to Reference) for all other missing data. The COVID-19 disruption is across the entire study and can be considered as random across subject characteristics and factors that may be related to treatment or outcome, so imputation assuming Missing at Random should be appropriate. Additional factors, such as the number of treatments received, can be added to the imputation model. Details to show that these subjects continued their visits up to the point of restrictions being imposed by the pandemic and did not discontinue treatment due factors related to the study protocol or outcome will be provided.
3. Impute all missing data from the control group (Jump to Reference).

In addition, last observation carried forward [LOCF] and observed cases [OC] will be used. The LOCF method will employ the last observation carried forward; this may be the baseline value if the subject has no follow-up values. The OC method will employ only observed cases for the time points of interest (i.e., for repeated measures analysis of Visit 6 [“Month 3”] and Visit 9 [“Month 6”] both mICARS must be observed/collected to be included in the analysis). A specific analysis using retrieved dropouts will not be performed (see [Section 5.10](#)).

Missing data for all other efficacy analyses not using MMRM will use Multiple Imputation #1 as described above), with the other imputation methods, LOCF and OC, for sensitivity.

Missing Values When Computing Instrument Scores

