5.3.1 Primary Efficacy Variable

The modified ICARS total score from the central rater (with speech domain scores from local raters) at baseline and each follow-up visit, and the change and percent change from baseline to each follow-up visit, will be summarized using descriptive summary statistics by treatment group.

The primary efficacy variable, change from baseline to follow-up (Visit 6 [“Month 3”] and Visit 9 [“Month 6”]) in mICARS total score (described above), will be analyzed using a mixed model repeated measures (MMRM) analysis, with the baseline mICARS value as covariate and five fixed effects (treatment, age [6 to <10 years, ≥ 10 years], sex, region, visit) and one interaction term (treatment-by-visit). The treatment effect, together with the associated two-sided 95% CI and p-value will be calculated. Unstructured covariance matrices will be used. Model effect estimation will be based on restricted maximum likelihood (REML). The region-by-treatment interaction can be tested in a separate model and if a significant interaction is found, then a forest plot will be used to present the region-specific treatment effects and associated 95% confidence intervals.

The primary MMRM analysis will assume missing at random (MAR) as a means of handling missing data.

Sensitivity analyses of these primary analyses will consist of ANCOVA at Visit 9 (‘‘Month 6’’) with missing data imputed using multiple imputations as described in [Section 5.1.3](#), LOCF, and OC. The results from each of the sensitivity analyses will be compared to the primary MMRM analysis.

When applying the multiple imputation methods describe in [Section 5.1.3](#), the regression method will be used, and the imputation model will be the same as the analysis model, based on the factors treatment, sex, age (category), region, and baseline mICARS; the pattern of missing data will be essentially monotonic since none of the factors used in the model are expected to be missing. One hundred iterations of the model will be run, and the results will be combined with SAS PROC MIANALYZE. For Multiple Imputation Method #2, multiple imputation based on subjects taking the same treatment will be applied first to the missing data due to COVID-19 related restrictions, and then Jump to Reference will be applied to the remaining missing data.

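### The SAP's observed-case (OC) rule in 5.1.3 asks for both Visit 6 and Visit 9, which contradicts the reason given in 5.10 for dropping the OC+RDO analysis and does not fit the Visit 9 ANCOVA in 5.3.1

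*SAP*

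**What the plan says.** **Protocol.** Section 16.2.8 plans three ANCOVA sensitivity analyses for the primary endpoint: LOCF, OC and OC+RDO. It says retrieved dropouts will be used in sensitivity analyses. It defines them as patients who stop treatment early but come back for the efficacy assessments at months 6, 9 and 12.

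**SAP 5.10** drops OC+RDO. It quotes the protocol definition and reasons that no RDO leaves any analysis population and that "since all have efficacy assessments at three of the four ICARS time points", Visit 6 being the one missing. From this it concludes that "they would be included in the OC analysis". It adds that RDOs without a Visit 6 ICARS simply contribute no Visit 6 value to OC, while "they will be included in the LOCF analysis". Its summing-up is: "Hence, the use of the LOCF and OC methods will sufficiently incorporate the RDO subjects".

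**SAP 5.1.3** repeats the decision ("A specific analysis using retrieved dropouts will not be performed") and refers to 5.10. In the same paragraph it describes OC as using only observed cases at the time points of interest. A parenthesis then explains that, for a repeated measures analysis of Visits 6 and 9, "both mICARS must be observed/collected to be included in the analysis".

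**SAP 5.3.1** gives the form of the analyses: "Sensitivity analyses of these primary analyses will consist of ANCOVA at Visit 9", with multiple imputation, LOCF and OC as the ways of handling missing data.

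**SAP 5.1.2** defines RDOs as early stoppers who return at Visits 6, 9, 12 and 15, which adds Visit 6 to the protocol's list.

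**The concern.** The patient whom 5.10 describes has Month 6 and lacks Month 3. That patient fails the both-visits condition in 5.1.3. So the SAP's one explicit OC inclusion rule for mICARS removes the patients whose presence in OC is part of the reason for not running OC+RDO.

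Three things are at stake. First, observed values at the primary time point would be discarded because a different visit is missing. Second, a departure from a protocol-specified analysis would rest on a statement that is untrue under the SAP's own rule. Third, two programmers could follow different sections and produce different OC tables (SAP 6.3.2, Tables 14.2.6.1 and 14.2.6.2). That choice should be settled before unblinding.

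**Working it through.** The plan states no figure on this point, so the check is to apply each rule to one patient: baseline observed, Visit 6 missing, Visit 9 observed.

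| Analysis and source | Is the patient's Visit 9 value used? |
|---|---|
| OC, both-visits condition (SAP 5.1.3) | No |
| OC as 5.10 describes it | Yes |
| OC as an ANCOVA at Visit 9 (SAP 5.3.1) | Yes; Visit 6 is not needed |
| LOCF (SAP 5.1.3, 5.10) | Yes; the observed Visit 9 value stands |
| Multiple imputation, methods 1 to 3 (SAP 5.1.3, 5.3.1) | Nothing in the text removes it |
| Primary MMRM (SAP 5.3.1) | Nothing in the text removes it |

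Rows 1 and 2 contradict each other. Row 1 also does not fit row 3: if OC is a Visit 9 ANCOVA, the repeated-measures wording in 5.1.3 has no planned OC analysis of mICARS to govern.

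The RDO definition changes the answer as well. Under the protocol definition quoted in 5.10 (months 6, 9 and 12), an RDO may lack Visit 6 and fail the both-visits condition. Under SAP 5.1.2 (Visits 6, 9, 12 and 15), an RDO has Visit 6 and passes it.

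**Illustration of size, with assumed counts.** The number of patients with Month 6 but no Month 3 is not given. I assume k = 0, 3 or 6 per arm; 6 is 10% of 60, borrowed from the loss-to-follow-up allowance only as a round upper figure. Other inputs are from SAP Table 3: 54 per arm, difference 3.0, SD 7.0, two-sided 0.05. For a two-group comparison at one visit, power = Φ(3.0 / (7.0 × √(2/n)) − 1.96) and the SE grows by √(54/n), with n = 54 − k.

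| k | n per arm | SE ratio | Power |
|---|---|---|---|
| 0 | 54 | 1.000 | Φ(2.227 − 1.96) = 60.5% |
| 3 | 51 | √(54/51) = 1.029 | Φ(2.164 − 1.96) = 58.1% |
| 6 | 48 | √(54/48) = 1.061 | Φ(2.100 − 1.96) = 55.6% |

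These are single-visit figures. They are not comparable with the 88.3% in Table 3, which is for two repeated measures. That 88.3% reproduces if the SD is multiplied by √((1 + ρ)/2) with ρ = 0: 7.0 × √0.5 = 4.95.

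The loss of precision is small. Which patients are analysed matters more. As an extreme assumption, suppose the k removed high-dose patients had no benefit and the rest had 3.0. OC with them estimates 3.0 × 51/54 = 2.83 (k = 3) or 3.0 × 48/54 = 2.67 (k = 6); OC without them estimates 3.0. The documents give no basis for choosing k or this zero effect.

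**The case against.** The best defence is that no patient is actually lost. The general OC statement in 5.1.3 refers to the time points of interest, the both-visits wording sits in a parenthesis about a repeated measures analysis, and 5.1.3 says the missing-data methods for efficacy are set out in full in 5.3. Section 5.3.1 makes the time point Visit 9. Section 5.10 also treats a missing Visit 6 as the loss of one visit's value, not of the patient. On that reading the patient stays in OC.

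This stands as a fair reading, and it is why the exclusion must be stated conditionally. It does not remove the problem: the parenthesis is written as an explanation of what OC means, so a programmer who follows it literally would exclude these patients.

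Second, 5.10 relies on LOCF and OC together, and LOCF keeps these patients. That also stands. A reader might infer that nothing is left in place of OC+RDO; the documents do not support that. Even under the strict rule, the patients are missing from one of five mICARS missing-data sensitivity analyses (three multiple-imputation methods, LOCF and OC).

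Third, under the RDO definition in SAP 5.1.2 the conflict would not arise for RDOs. That is correct, but 5.10 argues from the other definition, so this adds a second inconsistency to repair.

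**Conclusion.** The inconsistency is real and the SAP is wrong as written. The 5.1.3 condition cannot hold together with the OC statement in 5.10, and it does not match the analysis in 5.3.1. If it is applied, patients with Month 6 but no Month 3 drop out of OC, and the OC half of the reason for cancelling OC+RDO fails while the LOCF half holds.

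The size is unknown because the number of such patients is not given. Under the assumed 0 to 6 per arm, the SE of the OC comparison rises by at most about 6%. The effect is confined to one sensitivity analysis.

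A reader might go further and infer that the primary result is affected, or that the patients removed are mainly those with COVID-19 gaps or interrupted treatment. Neither is supported: nothing takes their Month 6 value out of the MMRM, and no document describes who misses Month 3 but attends Month 6.

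**What to change.** - In SAP 5.1.3, define OC for the Visit 9 ANCOVA as every FAS patient with a baseline and an observed Visit 9 mICARS, retrieved dropouts included, regardless of Visit 6. Delete the both-visits condition. The statement in 5.10 that these patients are in OC then becomes true.
- Use one RDO definition in 5.1.2 and 5.10, and state whether return at Visit 6 is required.

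The cost is a sentence or two in the SAP before unblinding. No new data and no additional analysis are needed.

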6. TABLES, FIGURES, AND LISTINGS

The mock tables, listings, and figures (including a TOC) will be presented in a separate document.

The general layout of the tables, figures, and listings (TFLs) will be as follows.

Orientation	Landscape
Paper Size	A4
Margins	Top: 3.2 cm Bottom: 2.5 cm Left: 2.5 cm Right: 2.5 cm
Font	Courier New 9 pt
Headers (alignment)	Sponsor name and Protocol number (Center) Page X of Y (Right) TFL Number and Title (Center)
Footers (alignment)	SAS program path and file name (Left) Date output generated (Right)

The font size may be reduced as necessary to allow additional columns to be presented, but not at the expense of clarity. Also, the orientation may be changed to portrait, if appropriate.

6.1 Preparation of Tables

Certain data will be collated into summary tables. A table of contents for the summary tables planned is presented in [Section 6.3](#). It may be necessary to change the table layouts, as appropriate, upon review of the data available.

6.2 Preparation of Data Listings

A table of contents, including the listing order and content of the data listing appendices, is presented in [Section 6.3](#). It may be necessary to change the listing layouts, as appropriate, upon review of the data available.

Data will be presented within the data listings according to the following order:

- Treatment group
- Subject number
- Visit

